9.3. Method of Assignment to Treatment

9.3.1. Phase 1

Patients who enter the study during the Phase 1 portion will be assigned to receive LY3039478 and dexamethasone. Prior to enrollment into the study, an eligibility check must be conducted (for every patient) between the investigational site and the Lilly clinical research personnel, to confirm that the patient meets all enrollment criteria. Upon confirmation of eligibility, the sponsor will confirm the dose, cohort, and identification number assignment for each patient. No dose escalations (ie, to the next cohort) can occur without prior discussion and agreement with the responsible Lilly CRP.

9.3.2. Phase 2

Patients who enter the study during the Phase 2 portion will be randomized to receive either LY3039478 in combination with dexamethasone or placebo in combination with dexamethasone. Assignment to treatment groups will be determined by a computer-generated random sequence using an interactive web-response system (IWRS).

A dynamic allocation method, introduced by Pocock and Simon (1975) and extended for unequal treatment group sizes by Han et al. (2009), will be adopted to balance patient assignment between treatment arms, using a probability factor of 0.9, based on the following factors:

- age \leq 30 years versus $>$ 30 years
- T-ALL phenotype versus T-LBL, considered as 6 factors, representing the following 5 phenotypes of T-ALL:

TdT+, variable for all of the following: CD1a, CD2, CD3, CD4, CD5, CD7, CD8, CD34

- Pro-T-ALL: cCD3+, CD7+, CD1a-, CD2-, CD4-, CD8-, CD34+/-
- Pre-T-ALL: cCD3+, CD7+, CD1a-, CD2+, CD4-, CD8-, CD34+/-
- Cortical T-ALL: cCD3+, CD7+, CD1a+, CD2+, CD4+, CD8+, CD34-
- Medullary T-ALL: cCD3+, sCD3+, CD7+, CD1a-, CD2+, CD4+or CD8+, CD34-
- ETP T-ALL: Lack of CD1a and CD8 expression, weak CD5 expression with less than 75% positive blasts, and expression of 1 or more of the following myeloid or stem cell markers on at least 25% of lymphoblasts: CD117, CD34, HLA-DR, CD13, CD33, CD11b, and/or CD65
- response to last therapy: refractory/relapse within 1 year of last therapy vs. $>$ 1 year

The randomization parameter P will be set to 0.9 to maximize the benefit of the allocation procedure, whilst keeping treatment assignments unpredictable.

The IWRS will be used to assign bottles containing double-blind study drug to each patient. Site personnel will confirm that they have located the correct bottles by entering a confirmation number found on the bottles into the IWRS.

9.4. Dose Adjustments and Delays

9.4.1. Dose Adjustments for LY3039478 within a Cycle

No dose adjustments of LY3039478 or placebo will be allowed within a cycle. If a patient treated at a given dose level experiences a DLT or a DLET (as defined in Section 9.2.2), then treatment will be suspended for that patient for the duration of the current cycle. If a toxicity does not meet the criteria for a DLT in Cycle 1 of Phase 1 (or a DLET in Cycle 2 and beyond in Phase 1 or any cycle in Phase 2) but nonetheless requires omission of dose(s) for tolerability, then dosing may resume at the same dose after the toxicity resolves to baseline; however, the dose(s) omitted for tolerability during a cycle will not be replaced.

9.4.2. Dose Adjustments for LY3039478 between Cycles

Before the start of each cycle, nonhematological toxicities (except alopecia and fatigue) must resolve to baseline. The start of LY3039478 may be delayed up to 21 days to allow sufficient time for recovery. Patients experiencing non-transient Grade 4 nonhematological toxicity or not recovering from toxicity within 21 days should be discontinued from the study.

The dose of LY3039478 should be reduced to the dose level administered in the previous cohort for all subsequent cycles of therapy if the investigator determines that it is in the best interest of the patient or if the patient experienced at least 1 of the following events:

- DLT (in Cycle 1 for patients in Phase 1)
- DLET (in Cycle 2 or beyond for patients in Phase 1, or in any cycle for patients in Phase 2)
- omission of more than 7 doses of LY3039478 in a single cycle for tolerability

For patients requiring a dose reduction, re-escalation to the original dose level is not permitted.

A second dose reduction is allowed only for patients treated at adult dose level ≥ 75 mg or pediatric equivalent (dose may be reduced to 25 mg or pediatric equivalent). Dose reduction by more than 2 dose levels is not permitted; patients requiring dose reduction by more than 2 dose levels should be discontinued from the study.

If a patient experiences a DLET at the second reduced dose level, then the patient will be discontinued from the study. If a patient requires omission of more than 3 doses for tolerability at the reduced dose levels, then treatment may continue if the investigator determines that the patient is receiving clinical benefit.

In the Phase 2 portion of the study, investigators will treat all patients as if the patient is receiving active study drug, LY3039478, and will adjust doses accordingly.

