5.1.6. Clinical Experience with LY3039478

As of April 2014, validated data from 39 patients in the first-in-human dose (FHD) Study I6F-MC-JJCA (JJCA) treated with LY3039478 in doses ranging from 2.5 mg to 60 mg are available. As of November 2014, LY3039478 doses of up to 100 mg have been explored. The MTD has been determined to be 75 mg.

Dose-limiting toxicities (DLTs) observed at dose levels of 20 mg, 30 mg, and 60 mg LY3039478 were thrombocytopenia Grade 4 in 1 patient in each dose group. Dose limiting toxicities at 100 mg included Grade 3 nausea (not manageable by medical treatment) and Grade 3 asthenia. In addition, 1 patient at 100 mg experienced Grade 2 colitis.

The most common adverse events (AEs) (>5% of patients) assessed as possibly related to study drug by the investigator included vomiting (41.0%); diarrhea (30.8%); asthenia, nausea, and hypophosphatemia (28.2%, each); decreased appetite (17.9%); hair color changes (15.4%); weight decreased (12.8%); thrombocytopenia, mucosal inflammation, alanine aminotransferase (ALT) increased, dry skin, and skin fissures (10.3% each); stomatitis and aspartate aminotransferase (AST) increased (7.7%, each); eyelash discoloration, dyspepsia, lipase increased, and dysgeusia (5.1%, each).

No Grade 5 Common Terminology Criteria for Adverse Events (CTCAE) events that were possibly related to study drug were reported. Grade 4 events possibly related to study drug included thrombocytopenia (3 patients, 7.7%) and increased lipase (1 patient, 2.6%). Grade 3 events possibly related to study drug included hypophosphatemia (5 patients, 12.8%) and colitis, asthenia, weight loss, and anorexia (1 patient each, 2.6%).

More information about the known and expected benefits, risks and reasonably anticipated AEs of LY3039478 can be found in the compound's IB. Information on AEs expected to be related to the investigational product can be found in Section 7 (Development Core Safety Information [DCSI]) of the IB. Information on serious adverse events (SAEs) expected in the study population independent of drug exposure and assessed by the sponsor in aggregate, periodically during the course of the study, can be found in Section 6 (Effects in Humans) of the IB.

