5.2. Rationale for Selection of Dose/Schedule and Design Discussion

The Phase 1 (Part A) portion of Study JJCB will assess escalating doses of LY3039478 when administered TIW in combination with 24 mg of dexamethasone given on Days 1 through 5 every other week. The TIW schedule for LY3039478 was selected based on the nonclinical toxicology and PK/PD data modeling and was explored in the FHD study, Study JJCA. The dose range to be explored in JJCB showed a decrease of a-beta as a PD marker in plasma (80%) and at least 50% inhibition of Notch target genes HES1, NRARP, and CCND1 in Study JJCA. The starting dose of 50 mg is below the MTD of 75 mg defined in Study JJCA as single-agent therapy. The administration schedule and fixed dose of 24 mg of dexamethasone have been chosen based on the current standard of care treatment of T-ALL/T-LBL. It is hypothesized that the combination of LY3039478 with dexamethasone will provide an active therapy option for adult patients with relapsed/refractory T-ALL/T-LBL disease.

The Phase 1 (Part B) portion of Study JJCB will assess escalation doses of LY3039478 when administered TIW in combination with dexamethasone in pediatric patients age 2 to <16 years. The starting dose for LY3039478 will be 80% of the initial dose administered to adults provided that no DLT is observed in the initial adult cohort and follows regulatory guidance as common practice. In addition, the administered dose of LY3039478 for pediatric patients will be calculated by body surface area (BSA). LY3039478 will be administered TIW. The

dexamethasone dose will be 10 mg/m² twice per day (BID) on Days 1 through 5 every other week.

The randomized Phase 2 portion of the study will assess LY3039478 at a dose defined in Phase 1 (Part A) given TIW in combination with dexamethasone versus placebo given TIW in combination with dexamethasone. Dexamethasone will be administered at a fixed dose of 24 mg on Days 1 through 5 every other week.

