Treatment with corticosteroids, such as dexamethasone, is part of the standard of care regimen for patients with ALL and LBL (Estey et al. 2008). Besides being a therapy against leukemic blasts by direct apoptotic effects and overcoming cytotoxic resistance, corticosteroids play a role in the supportive therapy of ALL. Dexamethasone can also provide protection against central nervous system (CNS) relapse of ALL. Even at relapse, most ALL patients retain sensitivity to dexamethasone. Patients with relapsed/refractory ALL progress quickly and require effective therapy, yet there is no established standard of care for relapsed T-ALL/T-LBL therapy. This study will combine dexamethasone with the active drug, LY3039478, to test efficacy. In addition, dexamethasone in combination with Notch inhibitors overcomes glucocorticoids resistance and mitigates GI toxicity.

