Safety data, in particular AEs, will be the primary criteria to allow for the dose escalation. The dose will be escalated following assessment of toxicity using the standard scoring system, CTCAE v 4.0, established by the NCI. Any AEs related to LY3039478 and/or dexamethasone will be considered as toxicities.

If available at the time of the dose-escalation decision, PK (eg, maximum observed concentration [C_{max}], AUC, and apparent systemic clearance) and PD results will be used as secondary/supporting data for dose escalation. No dose escalation can occur without prior discussion and agreement between the investigator and the Lilly CRP. The decision will be documented in writing. Intrapatient dose escalations are not permitted.

Based on the ongoing safety reviews, modifications to the dose-escalation strategy or other design elements may be made via protocol amendment to ensure patient safety.

[Table JJCB.9.2](#) shows the proposed dose levels for LY3039478 in combination with dexamethasone for the adult cohort. The starting dose level of 50 mg of LY3039478 was defined from Study JJCA and data will be evaluated on an ongoing basis until the MTD is determined. If the starting dose exceeds the MTD, a LY3039478 dose level (-1) may be explored. It should be noted that although an example escalation table is shown in [Table JJCB.9.2](#), alternate doses may be selected. Intermediate dose levels will be explored if deemed necessary after discussion between the sponsor and investigators and taking into account patient safety and PK/PD information.

Table JJCB.9.2. Proposed LY3039478 Dose-Escalation Scheme for the Adult Cohort

Dose Level	LY3039478 Dose (mg)	Dexamethasone Dose (mg)
-1 ^a	25	24
1	50	24
2	75	24

^a Dose level -1 to be used only in the event of dose-limiting toxicities experienced in dose level 1 necessitating a dose de-escalation.

The starting dose for pediatric cohort will be defined upon safety assessment of adult cohort. The starting dose will be 80% of total adult dose. Pediatric patients will be dosed based on BSA. Dose escalation will follow similar scheme to adult cohort.

By nature of being a dose-escalation study, data will be evaluated on an ongoing basis until the MTD is determined, as defined below.

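### Protocol 9.4.2 excepts alopecia but not hair or eyelash color change from recovery to baseline, so as written a cosmetic effect can postpone a cycle and, if it persists, lead to discontinuation

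*Protocol*

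**What the plan says.** Protocol Section 9.4.2 governs the start of each new cycle: "Before the start of each cycle, nonhematological toxicities (except alopecia and fatigue) must resolve to baseline". LY3039478 may be held for up to 21 days to allow recovery, and patients "not recovering from toxicity within 21 days should be discontinued from the study". The section gives no minimum grade and no clinical-significance qualifier. It also tells Phase 2 investigators to manage every patient as if on active drug, so the rule applies in both arms.

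The only general statement of what counts as a toxicity is in Section 9.2.1, on dose escalation: "Any AEs related to LY3039478 and/or dexamethasone will be considered as toxicities".

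Section 5.1.6 summarizes 39 patients in Study JJCA treated at 2.5 to 60 mg. Among adverse events judged possibly related to study drug in more than 5% of patients, it lists hair color changes (15.4%) and eyelash discoloration (5.1%). Alopecia is not in that list. Neither color change is named among the related Grade 3 or Grade 4 events; the Grade 3 sentence begins "Grade 3 events possibly related to study drug included hypophosphatemia" and goes on to colitis, asthenia, weight loss and anorexia.

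**The concern.** The exception list already accepts that one cosmetic hair effect, alopecia, should not hold up treatment. It omits the two cosmetic hair effects that the sponsor's own first-in-human data attribute to this drug. A site that follows the text would therefore hold LY3039478 for a patient whose hair or eyelashes have changed color, and would be directed to discontinue that patient if the color had not returned after 21 days.

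At stake is continuity of treatment for an individual patient who may be benefiting. Protocol Section 5.2 describes the setting: "Patients with relapsed/refractory ALL progress quickly and require effective therapy". Holding or stopping the drug for a change of color protects no one.

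**Working it through.** **1. Reproducing the JJCA counts.** Inputs from Section 5.1.6: n = 39, hair color changes 15.4%, eyelash discoloration 5.1%. With count = percentage × 39:

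- Hair color changes: 0.154 × 39 = 6.0, so 6 patients; check 6/39 = 15.4%.
- Eyelash discoloration: 0.051 × 39 = 2.0, so 2 patients; check 2/39 = 5.1%.

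Each is the only whole number out of 39 that rounds to the printed percentage. The overlap between the two events is not given. Patients with at least one therefore number between 6 (full overlap, 6/39 = 15.4%) and 6 + 2 = 8 (no overlap, 8/39 = 20.5%).

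**2. Does the rule reach these events?** Setting the sections side by side:

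- A related adverse event is a toxicity (9.2.1), and these events were judged possibly related (5.1.6).
- They are nonhematological and are neither alopecia nor fatigue (9.4.2).
- Section 8.3 ends the baseline period at the first study treatment, so a color change that appears on treatment is a departure from baseline.
- Section 9.4.2 sets no grade floor, so low grade does not exempt them.
- Section 9.4.2 does let treatment continue for clinical benefit, but only for patients who omit more than 3 doses at reduced dose levels. That clause is not attached to the recovery rule, and no other section of the protocol or SAP waives it.
- Waiting longer is not open either. Section 9.2 repeats the 21-day limit, and SAP Section 6.16 lists a cycle delay of more than 21 days, whatever the reason, as a protocol violation.

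So the literal reading covers both events. The 21-day stopping clause also does not repeat the exceptions in the opening sentence, so the two sentences should be tied together.

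**3. What follows for a patient.** If the color change is present when the next cycle is due, the start of LY3039478 moves by up to 21 days, a gap of up to 21/28 = 0.75 of a cycle length. If it is still present after 21 days, the text directs discontinuation.

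**4. What cannot be computed.** The probability of a delay is the probability that a color change occurs multiplied by the probability that it is present at a cycle start. The probability of discontinuation is that product multiplied by the probability that the change lasts beyond the 21 days. The documents inform only the first factor, and only for single-agent use at 2.5 to 60 mg. This trial adds dexamethasone and starts near the upper end of that range: "The starting dose of 50 mg is below the MTD of 75 mg defined in Study JJCA as single-agent therapy". Time to onset, duration and reversibility are not given, so no number of delays or discontinuations follows.

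**The case against.** The strongest case on the other side is that the strict reading is not the only one. The broad meaning of toxicity is taken from the dose-escalation section, and 9.4.2 does not refer to it. Section 7.3.1 lists unacceptable toxicity as a reason to stop study drug, which a color change would hardly be. Section 9.4.2 says such patients should be discontinued, whereas it says a patient with a dose-limiting equivalent toxicity at the second reduced dose will be. Most investigators would use common sense.

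Much of this stands, and it limits the point to wording. It does not remove it: the opening sentence says must, no competing definition is offered for 9.4.2, and naming alopecia and fatigue as exceptions suggests that low-grade events are otherwise included. An investigator who ignored a color change would be departing from the text, and sites could differ.

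A reader might also infer more than the documents support:

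- *That 15% to 20% of patients would be delayed or stopped.* The JJCA figures describe occurrence only, not presence at a cycle start or persistence beyond 21 days.
- *That a full delay costs 9 doses (3 weeks × 3 per week).* Sections 9.2 and 9.4.2 move the start of the cycle, and Section 8.1 sets no fixed treatment duration. For a patient who resumes, those doses are postponed. Only doses omitted within a cycle are stated not to be replaced (9.4.1).
- *That the primary endpoint or power suffers.* Randomized patients stay in the intention-to-treat set, and for T-ALL the Cycle 1 Day 28 marrow comes before any between-cycle delay. With no onset or duration data, no effect can be shown.

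Finally, the missing grade floor also catches low-grade dry skin and skin fissures (10.3% each) and dysgeusia (5.1%). That is true, but whether those should hold a cycle is a clinical judgment. Color change is the clear case, because the list already excuses alopecia.

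**Conclusion.** The point holds as a minor correction to a stated rule. Followed as written, Section 9.4.2 postpones LY3039478 by up to 21 days for a hair or eyelash color change present at the next cycle start, and directs discontinuation if the change persists beyond that. The effects are documented for this drug in 6 of 39 and 2 of 39 patients.

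The conclusion rests on applying the 9.2.1 meaning of toxicity to 9.4.2. Any consequence for a patient also depends on the change being present at a cycle start and, for discontinuation, on its persistence. Confidence is high about what the wording says. The documents do not allow an estimate of how often it would matter, and nothing is claimed about the overall remission rate or power.

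**What to change.** Make two small edits to Protocol Section 9.4.2:

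- In the opening sentence, change the parenthesis to *(except alopecia, hair or eyelash color change, and fatigue)*.
- In the 21-day stopping clause, after the word toxicity, insert *that is required above to resolve to baseline*, so that an excepted event cannot trigger discontinuation.

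Leave the rest of the section as it is, including the Grade 4 clause and return to baseline for all other toxicities, gastrointestinal effects among them. Do not add an open-ended investigator waiver. Whether to adopt a general threshold of Grade 1 or baseline, or to except other low-grade skin effects, is for the clinical team.

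The cost is two changes of wording and no new assessments. The downside is negligible, because only cosmetic color changes are newly exempted.

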9.4.3. Dose Adjustments – Dexamethasone

Dose adjustments for dexamethasone will be performed in case of toxicities that can't be controlled with appropriate treatment.

Toxicities and dose adjustments should be managed following available or institutional guidelines.

9.5. Blinding

The Phase 1b portion of this study is open-label whereas the Phase 2 portion of this study is double-blind.

To preserve the blinding of the study, a minimum number of sponsor personnel will see the treatment assignments before the study is complete.

Upon determination of relapsed/refractory disease or study completion, investigators and patients may be unblinded to study treatment assignment.

Phase 2 patients who discontinue the study due to relapse/refractory disease or treatment failure (Section 7.3.1) may be unblinded and cross over to treatment with LY3039478 in combination with dexamethasone if they had been randomized to receive placebo in combination with dexamethasone initially.

For this study, the following roles will be permitted to access unblinded data: all members of the assessment committee, plus unblinded statisticians and analysts, data scientists and PK/PD scientist. Access to unblinded data/documents will be controlled by restricting access to the data/documents in Lilly's data and statistical warehouse. Any changes to this unblinding plan may be described in a protocol amendment, the Statistical Analysis Plan (SAP), and/or a separate unblinding plan document. Interim analyses for safety, futility will be conducted, using unblinded data, under the guidance of an assessment committee. See Section 12.2.14 for further details.

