7.3. Discontinuations

7.3.1. Discontinuation of Patients

The criteria for enrollment must be followed explicitly. If a patient who did not meet enrollment criteria and was inadvertently enrolled is identified, either by the Sponsor or investigator, a discussion must occur between the Lilly CRP and the investigator to determine if the patient may continue in the study. The investigator must obtain documented approval from the Lilly CRP to allow the inadvertently enrolled patient to continue in the study with or without treatment with study drug. In addition, patients will be discontinued from the study drug in the following circumstances:

- enrollment in any other clinical trial involving an investigational product or enrollment in any other type of medical research judged not to be scientifically or medically compatible with this study
- investigator decision
 - the investigator decides that the patient should be discontinued from the study or study drugs
 - if the patient, for any reason, requires treatment with another therapeutic agent that has been demonstrated to be effective for treatment of the study indication, discontinuation from the study drug occurs prior to introduction of the new agent
- patient decision
 - the patient or the patient's designee (for example, parents or legal guardian) requests to be withdrawn from the study or study drug(s)
- sponsor decision
 - Lilly stops the study or stops the patient's participation in the study for medical, safety, regulatory, or other reasons consistent with applicable laws, regulations, and good clinical practice
- the patient is significantly noncompliant with study procedures and/or treatment
- unacceptable toxicity
- treatment failure in T-LBL or PD in T-ALL patients as described in Sections [10.1.3.1](#) and [10.1.3.2](#).

The reason for and date of discontinuation will be collected for all patients. All patients who received study drug will have procedures performed as shown in the Study Schedule ([Attachment 1](#)).

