After the last patient on Part A has completed Cycle 1 and the recommended dose for the Phase 2 portion is determined, the randomized, Phase 2 portion will begin following an interim review of the data as outlined in Section [12.2.14](#). The patient population in the Phase 2 portion of the study will be identical to the patient population assessed in Part A.

In the Phase 2 portion, 60 patients will be randomized in a 2:1 ratio to receive either LY3039478 in combination with dexamethasone administered 24 mg orally on Days 1 to 5 every other week or placebo in combination with dexamethasone administered 24 mg orally on Days 1 to 5 every other week. Placebo or LY3039478 will be administered orally TIW at the recommended dose from Part A. Patients will receive treatment until progression or meeting discontinuation criteria (Section [7.3](#)).

[figure not shown]
Patients discontinuing the study for treatment failure as defined in Section [7.3.1](#) will be unblinded after discontinuation. A crossover to LY3039478 in combination with dexamethasone will be allowed for patients who were receiving placebo in combination with dexamethasone.

A futility interim analysis will be performed in the Phase 2 portion of the study when 30 patients have completed the CR status determination. The analysis will assess the safety profile, verify that the chosen regimen is clinically feasible, and determine if the futility criteria have been met. See Section [12.2.14](#) for additional information on this futility interim analysis.

An internal assessment committee consisting of (at minimum) a Lilly Medical Director, a Lilly CRP not associated with the study, a PK scientist, and a statistician will examine the interim results and make recommendations about the trial.

The total sample size for this study is estimated to be approximately 86 to 92 patients.

There is no fixed duration of treatment; patients will remain on study until they fulfill 1 of the criteria for study discontinuation (Section [7.3](#)). Refer to [Attachment 1](#) for the Study Schedule.

¹ Phase 2 patients who discontinue the study due to relapse/refractory disease or treatment failure may crossover to treatment with LY3039478 + Dexamethasone.

Abbreviation: MTD = maximum tolerated dose.

Figure JJCB.8.1. Illustration of study design.

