Upon determination of treatment failure or study completion, investigators and patients may be unblinded to study treatment assignment. Patients with relapsed or refractory disease who were receiving placebo in combination with dexamethasone may crossover to LY3039478 in combination with dexamethasone and follow the "study period" treatment schedule.

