After the last patient on Part A has completed Cycle 1 and the recommended dose for the Phase 2 portion is determined, the randomized, Phase 2 portion will begin following an interim review of the data. The patient population in the Phase 2 portion of the study will be identical to the patient population assessed in Part A.

In the Phase 2 portion, 60 patients will be randomized in a 2:1 ratio to receive either LY3039478 in combination with dexamethasone administered 24 mg orally on Days 1 to 5 every other week or placebo in combination with dexamethasone administered 24 mg orally on Days 1 to 5 every other week. Placebo or LY3039478 will be administered orally TIW at the recommended dose from Part A. Patients will receive treatment until progression or meeting discontinuation criteria as outlined in the protocol.

[figure not shown]
Patients discontinuing the study for treatment failure will be unblinded after discontinuation. A crossover to LY3039478 in combination with dexamethasone will be allowed for patients who were receiving placebo in combination with dexamethasone.

A futility interim analysis will be performed in the Phase 2 portion of the study when 30 patients have completed the CR status determination. The analysis will assess the safety profile, verify that the chosen regimen is clinically feasible, and determine if the futility criteria have been met.

An internal assessment committee consisting of (at minimum) a Lilly Medical Director, a Lilly CRP not associated with the study, a PK scientist, and a statistician will examine the interim results and make recommendations about the trial.

The total sample size for this study is estimated to be approximately 86 to 92 patients.

There is no fixed duration of treatment; patients will remain on study until they fulfill 1 of the criteria for study discontinuation.

 Phase 2 patients who discontinue the study due to relapse/refractory disease or treatment failure may crossover to treatment with LY3039478 + Dexamethasone.

Abbreviation: MTD = maximum tolerated dose.

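### The trigger for unblinding and placebo crossover differs between sections, so Protocol 8.3 and 9.5 permit a crossover that SAP 6.16 lists as a violation

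*Protocol*

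**What the plan says.** Two triggers are in use.

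**Treatment failure only.** Protocol 7.3.1 lists, among the reasons to stop study drug, "treatment failure in T-LBL or PD in T-ALL patients as described in Sections" 10.1.3.1 and 10.1.3.2. The text of Protocol 8.1 carries this into unblinding: "Patients discontinuing the study for treatment failure as defined in Section" 7.3.1 are unblinded once they have discontinued. Protocol 8.3 has "Upon determination of treatment failure or study completion, investigators and patients may be unblinded to study treatment assignment". The SAP 5.1 text has "Patients discontinuing the study for treatment failure will be unblinded after discontinuation". SAP 6.16 lists as a study-specific violation any crossover for which failure on placebo is not documented.

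**Relapsed or refractory disease as well.** Protocol 9.5 has "Upon determination of relapsed/refractory disease or study completion, investigators and patients may be unblinded to study treatment assignment". Its next sentence allows unblinding and crossover for patients who discontinue for relapsed or refractory disease or treatment failure. The next sentence of 8.3 has "Patients with relapsed or refractory disease who were receiving placebo in combination with dexamethasone may crossover to LY3039478". The Figure JJCB.8.1 footnote covers patients who "discontinue the study due to relapse/refractory disease or treatment failure may crossover to treatment with LY3039478", and the matching SAP 5.1 footnote reads "Phase 2 patients who discontinue the study due to relapse/refractory disease or treatment failure may crossover to treatment with LY3039478".

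**Definitions.** Protocol 10.1.3.1 defines T-ALL treatment failure as progressive disease, and refractory T-ALL as not reaching CR, with no assessment time attached. For T-LBL, Table JJCB.10.1 defines treatment failure through relapsed or progressive disease; no definition of refractory T-LBL appears.

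**The concern.** This rule decides when the blind may be broken in a double-blind comparison and when a placebo patient may receive the test drug. If it depends on which section a site reads, two sites can treat the same patient differently and both be following the protocol. One of them will also have created a violation under the SAP.

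Timing matters because the primary endpoint is a best response. Under SAP 6.11.1 it accrues until progression or new anticancer therapy, and the analysis waits until patients have completed three cycles or left treatment. Unblinding someone who has not progressed and is still on treatment lets knowledge of the arm influence whether that patient stays long enough to respond. That is the bias the blind is there to prevent.

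**Working it through.** **Step 1. Set the triggers side by side.**

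| Place | Action governed | Treatment failure | Relapsed/refractory | Discontinuation required first |
|---|---|---|---|---|
| Protocol 7.3.1 | stopping study drug | yes (PD for T-ALL) | not listed | it is the discontinuation rule |
| Protocol 8.1 text | unblinding | yes | no | yes |
| Protocol 8.3, unblinding sentence | unblinding | yes | no | not stated |
| SAP 5.1 text | unblinding | yes | no | yes |
| SAP 6.16 | crossover (violation if unmet) | yes | no | not stated |
| Protocol 9.5, first sentence on this | unblinding | no | yes | not stated |
| Protocol 9.5, second sentence | unblinding and crossover | yes | yes | yes |
| Protocol 8.3, crossover sentence | crossover | no | yes | not stated |
| Figure JJCB.8.1 footnote | crossover | yes | yes | yes |
| SAP 5.1 footnote | crossover | yes | yes | yes |

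That is five places against five. Protocol 8.3 and SAP 5.1 each contain both versions.

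**Step 2. Check whether the terms are synonyms.** They are not. The censoring rules in SAP 6.11 list PD, relapsed disease and refractory as separate responses, next to CR, CRi and SD. Protocol 10.1.3.1 also gives refractory disease and treatment failure different definitions.

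**Step 3. Follow one patient.** A placebo T-ALL patient has the marrow examination at the end of Cycle 1 (Protocol 10.1.1.2) and shows neither remission nor progression.
- Protocol 8.1, the 8.3 unblinding sentence and the SAP 5.1 text: not a treatment failure, so no unblinding.
- First 9.5 sentence: refractory as defined, so may be unblinded, with no need to discontinue.
- 8.3 crossover sentence: may cross over. The second 9.5 sentence and both footnotes say the same once the patient discontinues, and 7.3.1 lets the investigator discontinue a patient by decision.
- SAP 6.16: that crossover is a violation.

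Best response is not settled at that point: neither progression nor new therapy has occurred, and the three-cycle horizon has not passed.

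**Step 4. How many patients the word could cover.** Inputs from Protocol 12.1: 40 and 20 patients, ORR 40% and 5%. Expected patients with neither CR nor CRi = n × (1 − ORR):
- LY3039478: 40 × 0.60 = 24
- placebo: 20 × 0.95 = 19
- total: 24 + 19 = 43 of 60

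This is a ceiling on expected exposure, not an effect. Non-remitters who progress meet both triggers, and the documents give no progression rate with which to remove them.

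**Step 5. Effect on ORR.** If unblinding comes first, mainly placebo patients have a reason to leave, and any late placebo remissions are lost; this favours LY3039478. If patients in both arms are taken off as refractory while still blinded, the arm with more remissions still to come loses more; this works against LY3039478. The balance depends on the timing of remission and on exit rates, which the documents do not give.

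False positives can be bounded without a timing assumption. Suppose the true ORR is 5% in both arms and every placebo remission is lost, giving 0 of 20. Two-sided Fisher then gives p = 0.084 for 7 of 40 against 0 of 20, and p = 0.043 for 8 of 40, so at least 8 responses are needed. The probability of 8 or more from a binomial with n = 40 and rate 0.05 is 0.0007, far below 0.05.

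**The case against.** Several points on the other side have force.

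- **Discontinuation usually comes first.** This is true of the second 9.5 sentence and both footnotes. It is not true of the first 9.5 sentence or the 8.3 crossover sentence, so the gap remains.
- **SAP 6.16 has limited consequences.** Its list feeds a listing and a summary. Crossover without failure is not among the per-protocol exclusions in SAP 6.6, and the primary analysis is ITT. This stands and limits the damage, but a permitted act is still listed as a violation.
- **Many non-remitters will progress quickly.** Protocol 5.2 describes rapid progression in this disease, so the two triggers will often coincide. This is fair, and the number left over is unknown.
- **Crossover is evidently later therapy.** Protocol 12.2.5 groups it with postdiscontinuation therapy, and SAP 6.1, 6.11 and 6.11.3 report crossover responses separately. This largely answers any worry that they would be credited to placebo. An explicit sentence would only clarify.

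A reader might infer three stronger things that the documents do not support.

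- **That CRi responders count as refractory**, because the T-ALL definition mentions only CR. SAP 6.11 keeps CRi and refractory as separate categories, so that reading should not be pressed.
- **That the conflict costs a definite amount of power.** Large losses would need blinded exit in both arms, which 7.3.1 already allows by investigator decision, together with an assumed timing of remission.
- **That the word refractory must be deleted.** Eligibility requires a life expectancy of only 2 months, and withholding crossover from placebo patients without remission is a real cost. Deletion is a choice for the sponsor.

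**Conclusion.** The inconsistency is real and the text is wrong as written. No reading satisfies all ten places for a placebo patient with neither remission nor progression, and the first 9.5 sentence opens the blind for that patient while the primary endpoint is still accruing. For T-ALL this follows directly from the definitions. For T-LBL the problem is that refractory has no definition at all.

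The size is limited to what the text shows: at the planned rates, at most 19 of 20 placebo patients (and 43 of 60 overall) are expected to be without remission, with an unknown share not progressing. Neither the direction nor the size of an effect on ORR can be determined, and no power figure should be attached. The conclusion on false positives rests on the planned 5% control ORR.

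**What to change.** 1. Use one trigger in Protocol 7.3.1, 8.1, 8.3, 9.5 and the Figure JJCB.8.1 footnote, and in SAP 5.1 (text and footnote) and SAP 6.16: documented treatment failure, relapse, or refractory disease. This means adding relapse and refractory disease to 7.3.1 and SAP 6.16.
2. Define refractory disease as neither CR nor CRi by a named assessment, separately for T-ALL and T-LBL, because their first response assessments fall at the end of Cycle 1 and Cycle 2 respectively.
3. Allow unblinding on any of these grounds only after the discontinuation decision and the response category have been recorded.
4. As a clarification, state in SAP 6.11.1 that the first crossover dose of LY3039478 ends best-response assessment for the randomized arm.

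The cost is wording in both documents and a short wait before unblinding while the response is recorded. No patients or procedures are added. If the sponsor prefers to drop refractory disease as a trigger, that also removes the conflict, but it may delay crossover for placebo patients with stable disease.
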